11.4 Descriptive Summaries of Efficacy Parameters

Absolute values and CFB values for all the continuous efficacy parameters will be summarized for all visits, including Week 6 (LOCF), by dose level (0.5, 0.75, and 1.0 *g* and overall) for the **Post-Amendment 3 ITT and PP populations and by treatment group (placebo and oxybutynin chloride gel) for the Pre-Amendment 3** ITT and PP populations using descriptive statistics including mean, 25th percentile, median, 75th percentile, SD, SEM, minimum, maximum, and number of *patients*. Additionally, the above descriptive summaries will be provided for each age group (*3 to* < *6 years*, 6 *to* < *12* years, 12 *to* < *17* years), for each weight category within *each* age group ($\leq 18 \text{ kg and} > 18 \text{ kg for the 3 to} < 6 \text{ years-of-age group}$, $\leq 25 \text{ kg and} > 25 \text{ kg for the } 3 \text{ to} < 6 \text{ years-of-age group}$.

6 to < 12 years-of-age group, and \leq 50 kg and > 50 kg for the 12 to < 17 years-of age group), and for each *sex*.

11.5 Statistical Analyses of Efficacy Parameters

All analyses will be conducted with SAS[®] v**9.3** or higher using procedures appropriate for the particular analysis.

11.5.1 Statistical Analysis of the Primary Efficacy Endpoint

The primary efficacy *parameter is the CFB to Week 6 (or LOCF) in the percentage of catheterizations without a leaking accident. The primary efficacy parameter* will be analyzed using an analysis of covariance (ANCOVA) model with the baseline measure of the primary variable as the covariate and treatment group *and study part (Pre-Amendment 3 and Post-Amendment 3) as factors.*

To assess the effect of the study design, the primary efficacy parameter will be analyzed using a random effects mixed model using the combined data from the Pre-Amendment 3 doubleblind treatment period and the data from the Post-Amendment 3 open-label treatment period. The model will include the baseline measure and other baseline characteristics as covariates and treatment (Pre-Amendment 3 double-blind placebo, Pre-Amendment 3 double-blind oxybutynin chloride gel, Post-Amendment 3 open-label oxybutynin chloride gel) as factors and will account for the heterogeneity between parts of the study (Pre-Amendment 3 vs Post-Amendment 3) by using a random effect for study part. If the analyses indicate heterogeneity, the data from the Pre-Amendment 3 double-blind treatment period and the data from the Post-Amendment 3 open-label treatment period will be analyzed separately. For the Post-Amendment 3 ITT population, the significance of the change from baseline on the primary efficacy measure will be assessed from a 2-sided, 1-sample t-test. For the Pre-Amendment 3 ITT population the primary efficacy parameter will be analyzed using an ANCOVA model with the baseline measure of the primary variable as the covariate and treatment group as factors.

11.5.2 Statistical Analysis of the Secondary Efficacy Endpoints

For the Post-Amendment 3 ITT population, the analyses of the secondary efficacy parameters will assess the CFB for each variable at Week 6 (LOCF). The significance of the change from baseline on the secondary efficacy measures will be assessed from 2-sided, 1-sample t-tests. For the Pre-Amendment 3 ITT population, secondary efficacy parameters will be analyzed using ANCOVA models with the baseline measure of the efficacy variable as the covariate and treatment group as factor.

11.5.3 Additional Analyses

The primary and secondary efficacy *endpoints* will be analyzed *at Week 6 LOCF*) for each of the per-protocol populations. The analyses will be similar to those described for the primary and secondary efficacy endpoint analyses.

The primary and secondary efficacy endpoints will be analyzed at each OC visit for *each of* the ITT and per-protocol populations. *The analyses will be similar to those described for the primary and secondary efficacy endpoint analyses.*

11.5.4 Subgroup Analyses

The primary and secondary efficacy data analyses will be analyzed separately for age groups, weight group, and *sex* group *for each ITT population*, as appropriate. Additionally, analysis of other important subgroups may be provided as well.

11.6 Safety Analysis

Safety variables will be summarized for *each* safety population using descriptive statistics and frequency distributions as defined in the following sections. Summaries will be provided overall and for each age group, weight group, and *sex* group.

11.6.1 Adverse Events

Key results will be presented for each safety population as follows:

- Post-Amendment 3 open-label safety population: by oxybutynin chloride gel dose level and/or overall
- Pre-Amendment 3 double-blind safety population: by treatment group and/or treatment and dose level, and/or overall
- Pre-Amendment 3 open-label safety population: by treatment group in the lead-in double-blind period and overall
- Combined open-label safety population: by oxybutynin chloride gel dose level and/or overall

The incidence of treatment-emergent adverse events will be summarized for the safety populations *as described above*. Adverse events will be coded using Medical Dictionary for Regulatory Activities (MedDRA) terminology. Summaries of the following types will be provided:

- Overall summary of treatment-emergent adverse events
- Summary of treatment-emergent adverse events by MedDRA system organ class, MedDRA preferred term, *study treatment* relationship, and *severity*
- Summary of serious treatment-emergent adverse events by MedDRA system organ class, MedDRA preferred term, *study treatment* relationship, and *severity*
- Summary of treatment-emergent adverse events by MedDRA preferred term and *study treatment* relationship in descending order
- Summary of treatment-emergent adverse events by MedDRA system organ class, MedDRA preferred term, and *study treatment* relationship for events leading to premature discontinuation from the study

These summaries will present the number and percentage of *patients* reporting an adverse event for each classification level as well as the number of events reported. The denominators for calculating the percentages will be based on the number of *patients* in *each* safety population for each *tabulated* group.

All adverse events, *SAEs*, deaths, *SAEs* considered to be related to treatment, and adverse events leading to premature discontinuation from the study will also be provided in data listings.

11.6.2 Extent of Exposure

Summaries for duration of exposure for *each* safety population will be provided by treatment group for the *Pre-Amendment 3 double-blind* period, and by exposure to *oxybutynin chloride gel* for *each of* the *Pre-Amendment 3 and Post-Amendment 3 open-label* periods *and the Pre-Amendment 3 double-blind* and *open-label* periods combined. Duration of exposure to study *treatment* will be summarized using descriptive statistics (mean, 25th percentile, median, 75th percentile, SD, SEM, minimum, maximum, and number of *patients*). Duration of exposure will be calculated as the difference between the last dose date and the first dose date plus 1 day.

Additionally, these summaries will present the number and percentage of *patients* for each interval (1-week multiples) of total exposure. The denominators for calculating the percentages will be based on the number of *patients* with exposure.

11.6.3 Laboratory Evaluations and Abnormalities

Continuous clinical laboratory analytes will be summarized for *each* safety population by *double-blind* period treatment group, double-blind treatment/*oxybutynin chloride gel* sequence, or *oxybutynin chloride gel* only, *as applicable, and by* analyte and visit using descriptive statistics (mean, 25th percentile, median, 75th percentile, SD, SEM, minimum, maximum, and number of *patients*). Categorical laboratory analytes, classified as normal or abnormal, will be summarized for *each* safety population by DB treatment group *or oxybutynin chloride gel only group as applicable, and* analyte and visit using the number and percentage of *patients* in each category. The denominators for calculating the percentages will be based on the number of *patients* in each treatment group or *oxybutynin chloride gel* only group, *as applicable*, with nonmissing assessments at a particular visit for *each* safety population.

Shifts to values outside of the normal range will be presented as described above by summarizing the number and percentage of *patients* with evaluable shifts. An evaluable shift is one where both the baseline value (screening value) and the *Pre-Amendment 3* Week 14 or *Post-Amendment 3 Week 14 or* ET values are recorded. The denominators for calculating the percentages will be based on the number of *patients* in each treatment group, *double- blind treatment/ oxybutynin chloride gel sequence*, or *oxybutynin chloride gel* only, *as applicable* who have an evaluable shift for a particular analyte. Evaluable shifts to be presented are $N \rightarrow L$, $N \rightarrow H$, $H \rightarrow L$, $H \rightarrow N$, $L \rightarrow H$, and $L \rightarrow N$ for continuous variables and normal \rightarrow abnormal for categorical variables.

All clinical laboratory values, abnormal clinical laboratory values, and clinically significant laboratory values will also be provided in data listings.

11.6.4 Vital Signs

Vital sign measurements will be summarized for *each* safety population by treatment group, double-blind *treatment/ oxybutynin chloride gel sequence*, or *oxybutynin chloride gel* only *group, as applicable*, and visit using descriptive statistics (mean, 25th percentile, median, 75th percentile, SD, SEM, minimum, maximum, and number of *patients*). In addition, descriptive statistics will be presented for change from baseline (baseline is defined as Week 0 *[Visit 2 for Pre-Amendment 3 and Visit B for Post-Amendment 3]*) for systolic and diastolic blood pressures and heart rate.

11.6.5 Physical Examinations

Physical examination assessments will be summarized for *each* safety population by DB treatment group *or oxybutynin chloride gel* only *group, as applicable,* and visit. For each body system and assessment category, the number and percentage of *patients* will be presented. The denominators for calculating the percentages will be based on the number of *patients* evaluated for each body system.

11.6.6 Skin Assessments for Erythema

Skin assessments for erythema will be summarized for *each* safety population by treatment group and visit for the *Pre-Amendment 3 double-blind* period and by *oxybutynin chloride gel* only and visit for the *Pre-Amendment 3 open-label* period, *the Pre-Amendment 3 double-blind* and *open-label* periods combined, *and the Post-Amendment 3 open-label period*. Additionally, skin assessments for erythema will be summarized over all visits for each of the above described summaries. Summaries will present the number and percentage of *patients* for each erythema category (none, mild, moderate, and severe). The denominators for calculating the percentages will be based on the number of *patients* with nonmissing assessments.

11.7 Other Assessments

11.7.1 Demographic and Other Pretreatment Characteristics

Patient demographic and physical characteristic data *and* medical history data will be summarized for each analysis population using descriptive statistics (mean, 25th percentile, median, 75th percentile, SD, SEM, minimum, maximum, and number of *patients*) for continuous variables and frequency distributions (number and percentage of patients) for categorical variables. Patient demographic data *Pre-Amendment 3* will be summarized by *double-blind* period treatment group and overall for the *double-blind* period and by *oxybutynin chloride gel* only for the *open-label* period and *double-blind* and *open-label* periods combined. Medical history data will be summarized by *double-blind* period treatment group and overall for *double-blind* period and by *oxybutynin chloride gel* only for the *open-label* period and *doubleblind* and *open-label* periods combined. *Post-Amendment 3 patient demographic and medical history data will be summarized by oxybutynin chloride gel level and overall*.

11.7.2 Medications

Medication usage will be coded using World Health Organization Drug Dictionary Enhanced Anatomical/Therapeutic/Chemical classification. Summaries of medications will be presented for the safety population by anatomical and therapeutic category and preferred name.

Pre-Amendment 3, summaries for the double-blind period will be provided by treatment and overall, and summaries for the open-label period and the double-blind and open-label periods combined will be provided for the oxybutynin chloride gel only group. Prior medication use and concomitant (on or after the first day of treatment) medication use will be documented and summarized separately. If the end date of prior medication occurs after treatment starts, then the medication will be reported as both prior and concomitant in the summaries. Summaries for Post-Amendment 3 will be provided by oxybutynin chloride gel dose level and overall.

11.7.3 Compliance

Compliance with the *study treatment* for each patient/visit will be calculated using the following formula:

Compliance = $\left(\frac{\text{\# of sachets dispensed} - \text{\# returned}}{\text{\# expected}}\right) * 100$

The expected number of sachets to be used for each patient will be based on the total number of treatment days. Compliance will be summarized by visit and over all visits using descriptive statistics (mean, 25th percentile, median, 75th percentile, SD, SEM, minimum, maximum, and number of *patients*) for the *Pre-Amendment 3 double-blind* safety population. Compliance will be summarized for the *open-label* periods by visit and over all visits using the same descriptive statistics.

11.7.4 Urodynamic Variables

Urodynamic variables will be summarized for the *Pre-Amendment 3 double-blind and Post-Amendment 3* safety populations. *Results will be presented* by treatment group and visit and by treatment group, dose level, and visit for the *Pre-Amendment 3 double-blind* period *and by oxybutynin chloride gel only and visit for the post-Amendment 3 open-label period* using descriptive statistics (mean, 25th percentile, median, 75th percentile, SD, SEM, minimum, maximum, and number of *patients*) for continuous variables and frequency distributions (number and percentage of *patients*) for categorical variables. Summaries will be provided overall and for each age group and *sex*. In addition, descriptive statistics will be presented for change from baseline (baseline is defined as Week 0) for continuous urodynamic variables.

11.7.5 Anticholinergic Symptoms Questionnaire

Anticholinergic symptom questionn*aire data* will be summarized for the *Pre-Amendment 3 double-blind* safety population by treatment group and visit and by treatment group, dose level, and visit for the *double-blind* period. Anticholinergic symptom questionnaire data will be summarized by *oxybutynin chloride gel* only and visit and by *oxybutynin chloride gel* only, dose level, and visit for the *Pre-Amendment 3 open-label* period and the *Pre-Amendment 3 double-blind* and *open-label* periods combined, *and for the Post-Amendment 3 open-label period*. Summaries will be provided overall and for each age group and sex. Summaries will present the number and percentage of *patients* for each category. The denominators for calculating the percentages will be based on the number of *patients* with nonmissing values in each treatment group or *oxybutynin chloride gel* only group, *or dose level* and visit, *as applicable*. Additionally, shifts from baseline (baseline is defined at Week 0) for each question will be provided for all evaluable shifts. An evaluable shift is one where both the baseline evaluation and on-treatment evaluations are recorded.

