This study was initiated as a double-blind, placebo-controlled study with an open-label extension, and amended to enroll patients under only open-label treatment. Prior to Amendment 3, patients aged 6 years to < 17 years were randomly assigned 1:1 to receive double-blind oxybutynin chloride gel or placebo gel for 6 weeks, followed by an open-label, 8-week period to generate safety data. All patients began treatment with 0.75 g of gel/day for 2 weeks. Patients then returned to the clinic for a potential dose titration and at this time their dose could have been adjusted up to 1 g/day, down to 0.5 g/day, or remained the same at 0.75 g/day. The determination of dose was based on the investigator's clinical judgment and assessment of the patient's bladder symptoms and treatment side effects. Dose titration was permitted only once during the entire 6-week double-blind, placebo-controlled period. Patients continued blinded treatment for 4 additional weeks until the end of the double-blind treatment period.

Post-Amendment 3, the study dose-titration study in pediatric patients, ages 3 years to < 17 years, with detrusor overactivity associated with a neurological condition. Efforts will be made to enroll a greater number of patients from the ages of 3 years to < 6 years. Patients must be suitable candidates for anticholinergic therapy and must be using clean intermittent catheterization (CIC) for bladder control. The study will include a screening period from Day -13 to Day -5 and a 14-week open-label treatment period. The expected duration of the study for each patient will be up to 16 weeks. No changes were made in the starting dose, compared to the Pre-Amendment 3 study design, in that all patients will begin treatment with 0.75 g of gel/day for 2 weeks. Patients will then return to the clinic for a potential dose titration and at this time their dose may be adjusted up to 1 g/day, down to 0.5 g/day, or remain the same at 0.75 g/day, depending on individual response and tolerability. The determination of dose will be based on the investigator's clinical judgment and assessment of the patient's bladder symptoms and treatment side effects. Dose titration will be permitted only once during the entire 14-week treatment period. Patients will continue the adjusted dose for 12 additional weeks until the end of the open-label treatment period.

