9.4 Study Treatments

9.4.1 Treatments Administered

Pre-Amendment 3, patients were randomized to receive oxybutynin chloride gel or placebo during the 6-week double-blind treatment period, and all patients received oxybutynin chloride gel during the 8-week open-label treatment period. Patients randomized to double- blind oxybutynin chloride gel started treatment at 0.75 g/day, and the dose may have been adjusted after 2 weeks of treatment to a higher or lower dose (0.5 g/day or 1 g/day) based on the investigator's clinical judgment and assessment of bladder symptoms and treatment side effects. All patients who entered the open-label safety period were started on 0.75 g/day oxybutynin chloride gel, and the dose may have been adjusted after 2 weeks of treatment as described for the double-blind treatment period.

Post-Amendment 3, no changes were made in the starting dose, compared to the Pre-Amendment 3 study design, in that all patients will begin treatment with 0.75 g of gel/day for 2 weeks. Patients will then return to the clinic for a potential dose titration and at this time their dose may be adjusted up to 1 g/day, down to 0.5 g/day, or remain the same at 0.75 g/day, depending on individual response and tolerability. The determination of dose will be based on the investigator's clinical judgment and assessment of the patient's bladder symptoms and treatment side effects. Dose titration will be permitted only once during the entire 14-week treatment period. Patients will continue the adjusted dose for 12 additional weeks until the end of the open-label treatment period. *Patients* or parents/*caregiver* will apply the gel each morning to rotating application sites on the abdomen, upper arms/shoulders, and thighs. The person who applies the gel should wash *his or her* hands immediately after application with soap and water.

Patients should not bathe or shower sooner than 1 hour following a gel application. In the event of direct contact between unwashed or unclothed skin to which gel has been applied and the skin of another person, the contact area on the other person should be washed with soap and water as soon as possible.

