5.1.1.4 Safety Analyses

Safety analyses will be based on each safety population.

Baseline assessments for applicable safety endpoints defined as follows:

Table 5-13 Safety Endpoint Baseline Definitions

Parameter	Description	Timing
Clinical laboratory evaluations	eCRF- or (standardized) vendor-provided	Latest non-missing
 Vital signs 	assessments	assessment
 Physical Examination 		on/before treatment
Skin Assessments for		start date
Erythema		

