5.1.1.4.4 Vital Signs

Vital signs will be summarized by treatment group, double-blind treatment/oxybutynin chloride gel sequence, or oxybutynin chloride gel only group, as applicable, and visit for each safety population as follows:

Table 5-19 Vital Signs Summaries

Endpoint	Description	Timing	Methodology
Descriptives	Summary of change from baseline by	Pre-Amendment 3	CFB
	parameter and analysis visit	Weeks 1 to 6; Post-	descriptives
	Parameters specified in Section 6.4.3.1	Amendment 3 Visits	
		B, C, D, E, and F ¹	
Descriptives	Summary of raw values by parameter and	Pre-Amendment 3	Continuous CFB
	analysis visit	all double-blind	descriptives
	Parameters specified in Section 6.4.3.1	visits; Post-	
		Amendment 3 Visits	
		A, B, C, D, E, and	
		F^1	
Descriptives	Summary of raw values and change from	Combined open-	Continuous CFB
	baseline by parameter and analysis visit	label period	descriptives
	Parameters specified in Section 6.4.3.1		

¹ Analysis visits defined in Section 6.2.2.

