5.1.1.5 Other Assessments

5.1.1.5.1 Anticholinergic Questionnaire

Anticholinergic symptom questionnaire data will be summarized for the Pre-Amendment 3 double-blind safety population by treatment group and visit and by treatment group, dose level, and visit for the double-blind period. Anticholinergic symptom questionnaire data will be summarized by oxybutynin chloride gel only and visit and by oxybutynin chloride gel only, dose level, and visit for the Pre-Amendment 3 open-label period and the Pre-Amendment 3 double-blind and open-label periods combined, and for the Post-Amendment 3 open-label period.

Additionally, shifts from baseline for each question will be provided for all evaluable shifts. An evaluable shift is one where both the baseline evaluation and on-treatment evaluations are recorded.

Table 5-22 Anticholinergic Questionnaire Summaries

Endpoint	Endpoint Description		Methodology
Each question on the	Each question on the Categorical summary of number and		Categorical
questionnaire1 overall	percentage of participants in a response	Weeks 0, 6, and 14;	descriptives
and by age group and	category (no, mild, tolerable, or	Post-Amendment 3	
sex	intolerable, applicable) by question and	Visits B, C, D, E,	
	analysis visit; shift tables summarizing	and F ²	
	the shift in categorical response from		
	baseline to each post-baseline visit (for		
	Pre-Amendment 3 and also for Post-		
	Amendment 3)		

- 1 Participants who have non-missing assessments.
- 2 Analysis visits defined in Section 6.2.2.

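### In the Pre-Amendment 3 gel-only anticholinergic questionnaire tables, the Week 0 baseline puts six placebo weeks into the Week 14 shift of children who started on placebo

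*Protocol*

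**What the plan says.** **Design.** Before Amendment 3, children were "randomly assigned 1:1 to receive double-blind oxybutynin chloride gel or placebo gel for 6 weeks" (protocol synopsis). Afterwards "all patients received oxybutynin chloride gel during the 8-week open-label treatment period" (protocol 9.4.1).

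**Questionnaire.** Protocol 11.7.5 sets a single baseline: "shifts from baseline (baseline is defined at Week 0) for each question will be provided for all evaluable shifts". On grouping, SAP 5.1.1.5.1 reads: "summarized by oxybutynin chloride gel only and visit and by oxybutynin chloride gel only, dose level, and visit for the Pre-Amendment 3 open-label period". It does the same for the two Pre-Amendment 3 periods combined. SAP Table 5-22 adds shift tables from baseline to each later visit. Neither document splits these gel-only tables by double-blind arm. SAP Table 5-13, which defines safety baselines, does not list the questionnaire. SAP Table 6-4, which covers safety and other assessments, has one Pre-Amendment 3 baseline row, at Visit 1/Visit 2.

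**Vital signs.** Protocol 11.6.4 says "descriptive statistics will be presented for change from baseline (baseline is defined as Week 0", and names Visit 2 for Pre-Amendment 3 and Visit B for Post-Amendment 3. SAP Table 5-13 takes the latest non-missing value "on/before treatment" start, without saying which period's start. On grouping, SAP 5.1.1.4.4 reads: "Vital signs will be summarized by treatment group, double-blind treatment/oxybutynin chloride gel sequence, or oxybutynin chloride gel only group, as applicable".

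**The concern.** A gel-only shift table is meant to show what happened after children began gel. For a child who was on placebo first, Week 0 lies six weeks before the first gel dose. A symptom that appeared on placebo and persisted is then displayed as a shift on gel. The error can also run the other way: a symptom present at Week 0 that cleared by Week 6 and came back on gel is displayed as no change.

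Safety is a stated secondary objective, and the questionnaire asks specifically about anticholinergic side effects. A reader of the gel-only table could not tell which part of a shift preceded gel.

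**Working it through.** The plan gives no figure to reproduce here. The check is of definitions first, then of how much could be carried over.

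**1. Where the last pre-gel questionnaire lies.** Protocol 9.8.5 and SAP Appendix 1 place the Pre-Amendment 3 questionnaire at Visits 2, 6 and 8 (Weeks 0, 6 and 14). Protocol 9.5.2.1 places the Post-Amendment 3 baseline questionnaire at Visit B, before the first dose.

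| Group | Last questionnaire before gel | Baseline in the plan | Placebo weeks inside the Week 14 shift |
|---|---|---|---|
| Lead-in gel | Visit 2 (Week 0) | Week 0 | 0 |
| Lead-in placebo | Visit 6 (Week 6) | Week 0 | 6 |
| Post-Amendment 3 | Visit B | Visit B | 0 |

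Only the lead-in placebo row is wrong. Visit 8 is the only scheduled open-label questionnaire before Amendment 3, so the affected result is the Week 14 shift.

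**2. Whether the SAP settles it differently.** SAP Table 6-1 resets Day 1 to the first open-label dose, which might suggest an open-label baseline. SAP Table 6-4 provides no such row. If Visit 6 were used for everyone, lead-in gel children would have a baseline taken on gel. No single calendar visit is the last pre-gel value for both arms.

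**3. What the Week 14 shift contains for lead-in placebo children.**

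change(Week 0 to 14) = change(Week 0 to 6, placebo) + change(Week 6 to 14, gel)

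**4. Share of such children.** With the planned 96 children, 1:1 allocation and equal continuation into open-label treatment (assumed), w = 48/96 = 0.50.

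**5. Part of the pooled shift rate that arose on placebo.** Let p be the proportion of placebo children who shift by Week 6 and are still shifted at Week 14. The documents do not give p, so it is assumed over a range. Percentage points carried = 100 × w × p.

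- p = 0.05: 100 × 0.50 × 0.05 = 2.5
- p = 0.10: 100 × 0.50 × 0.10 = 5.0
- p = 0.20: 100 × 0.50 × 0.20 = 10.0

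This is the part of the displayed rate with onset before gel. It is not a net bias, because some of these children might have developed the symptom on gel anyway.

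**6. Vital signs.** SAP Table 5-19 plans change from baseline for three things: Pre-Amendment 3 Weeks 1 to 6, Post-Amendment 3 visits, and the combined open-label period. Only the last pools former placebo children with others after they start gel. With 96 children before and 25 after Amendment 3, their share is 48/(96 + 25) = 0.40. With only 25 before (assumed low case), it is 12.5/(25 + 25) = 0.25. On a Week 0 baseline, the pooled mean change would carry about 0.25 to 0.40 times the mean placebo-period change.

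**The case against.** **Adverse events are already assigned by period.** This stands. Anticholinergic adverse events found on the questionnaire go on the Adverse Event Form (protocol 9.8.5). SAP Table 5-15 assigns an event that starts before the first open-label dose to the double-blind period. Protocol 11.6.1 also presents Pre-Amendment 3 open-label events by lead-in group, although SAP 5.1.1.4.2 lists dose level and overall instead. The questionnaire is a descriptive assessment with no test. A reader might infer that the trial's main safety read-out is distorted; the documents do not support that.

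**Vital signs.** A reader might infer that they are affected as widely as the questionnaire. They are not. Both documents allow presentation by treatment sequence, which would show placebo-to-gel children separately, and the SAP baseline is ambiguous rather than fixed at Week 0. The exposure is confined to the combined open-label change.

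**Pooling with Post-Amendment 3 children.** This does not arise for the questionnaire. Protocol 11.7.5 and SAP 5.1.1.5.1 list the Post-Amendment 3 period separately, and Table 5-22 gives shifts for each part.

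**A definite inflation of the gel rate.** It is tempting to compare a Week 0 result with a true gel rate, but that needs background symptoms in placebo children and none in gel children over the same weeks. Suppose 90% are symptom-free at Week 0, 10% of all children acquire a background symptom by Week 6, and gel adds a symptom in 20% of those still free. Lead-in placebo then shows (0.10 + 0.80 × 0.20)/0.90 = 28.9%. Lead-in gel with the same background shows 1 − 0.80 × (0.80/0.90) = 28.9%. The defect is one of attribution, and no net inflation can be derived from the documents.

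**The double-blind tables show placebo shifts at Week 6.** True, but as a separate margin. They do not say which children's Week 14 shifts began on placebo.

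**The gel-only label is undefined.** It might mean children who received gel throughout. However, every child received gel in the open-label period, and nothing excludes former placebo children from that table.

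**Re-baselining mixes follow-up lengths.** This stands. Lead-in gel children would have 14 weeks of gel and lead-in placebo children 8, so a changed baseline alone is not enough.

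**Conclusion.** The point holds for the Pre-Amendment 3 gel-only questionnaire shift tables: the open-label period, and the double-blind and open-label periods combined. Following the stated rule, the Week 14 shift of lead-in placebo children includes six weeks on placebo, although a pre-gel value at Week 6 is scheduled. For vital signs it holds only for the combined open-label change, and there as an ambiguity to be settled. Lead-in gel and Post-Amendment 3 children are not affected.

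The size is unknown. The 2.5 to 10 percentage points rest on an assumed 5% to 20% persistent shift rate on placebo, planned enrolment, and equal continuation from both arms. The consequence is for descriptive safety interpretation only. It is worth correcting because the correction is simple.

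**What to change.** - **Questionnaire (protocol 11.7.5; SAP 5.1.1.5.1 and Table 5-22).** For the Pre-Amendment 3 gel-only tables, define baseline as the last non-missing value before the first gel dose: Visit 2 for lead-in gel, Visit 6 for lead-in placebo. Present the shifts by lead-in arm, with a footnote giving the 14 and 8 weeks of gel follow-up. Keep Week 0 for the double-blind gel-versus-placebo tables.
- **Vital signs (SAP Tables 5-13 and 5-19).** State which treatment start Table 5-13 means. Use the last pre-gel value for the combined open-label change.
- **Consistency.** Add the questionnaire to Table 5-13 and a matching baseline rule to Table 6-4. Reconcile both with Table 6-1 and protocol 11.6.4. Define the gel-only group.

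The cost is SAP wording, a protocol clarification and one derived baseline flag; no new data are needed. The split makes columns smaller, especially by dose level. A lead-in or sequence grouping is already in the protocol for adverse events (11.6.1), laboratory data (11.6.3) and vital signs (11.6.4), so it adds no new kind of display. The change should be made before database lock.
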